3.3 Sample size

This phase 2 trial is launched before we obtaining the immunogenicity data from the phase 1 trial. Therefore, the sample size of is not calculated, but determined based on expert experiences and the minimum sample size requirement in the technical guidelines for vaccine clinical trials issued by National Medical Products Administration, China. The final sample size is 250 in the middle dose group, 125 in

the low dose group and 125 in the placebo group, with a total sample size of 500.

The antibodies of all participants are measured by ELISA at day 0, day 14, day 28 and month 6, and the antibodies of participants are measured by live SARS-CoV-2 or pseudovirus neutralization test at day 0, day 28, and month 6.

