5.2.2 Immunogenicity endpoint

- Geometric mean titer (GMT) of antigen-specific antibody at day 14, and month 6 measured by ELISA.

- Geometric mean titer (GMT) of specific neutralizing antibody against SARS-CoV-2 at month 6 after immunization measured by live SARS-CoV-2 and pseudovirus neutralization test.
- Seroconversion rate of antigen-specific antibody at day 14, day 28, and month 6 measured by ELISA.
- Geometric mean fold increase (GMI) of antigen-specific antibody at day 14, day 28, and month 6 measured by ELISA.
- Seroconversion rate of specific neutralizing antibody against SARS-CoV-2 at day 28, and month 6 measured by live SARS-CoV-2 and pseudovirus neutralization test.
- Geometric mean fold increase (GMI) of specific neutralizing antibody against SARS-CoV-2 at day 28, and month 6 measured by live SARS-CoV-2 and pseudovirus neutralization test.
- Geometric mean titer (GMT) of neutralizing antibody against Ad5 at day 28, and month 6.
- Geometric mean fold increase (GMI) of neutralizing antibody against Ad5 at day 28, and month 6
- The positive rate and level of IFN- γ stimulated by S protein overlapping peptide library at day 28 measured by ELISpot.

For uncertain values: when calculating GMT, GMI and seroconversion of antibodies, if the antibody level is below the initial detection limit, half of the initial value will be used; if the antibody level is greater than the detection limit, the maximum dilution will be used.

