8.1 General principles

In this study, the statistical analysis will be completed by SAS 9.4 ®software, and part of the statistical charts will be completed by SPICE 6. The related database is exported and saved in SAS XPORT format.

The statistical analysis plan is formulated by biostatisticians and the principal

investigator according to the protocol, and the final document is refined and formed before the data is locked.

- Continuous variables will be described by mean, standard deviation, median, quartile, minimum, maximum, and coefficient of variation.
- The categorical and ranked data will be described by frequency and percentage.
- The continuous variables will be analyzed by analysis of variance. When the test level is $\alpha=0.05$ and $P\leq 0.05$, the difference will be considered to be statistically significant, and the pairwise comparison will be made by SNK method.
- Chi-square test will be used to classify the categorical variables, and the difference is considered to be statistically significant when the test level is $\alpha=0.05$ and $P\leq 0.05$. the chi-square partition method will be used for pairwise comparison, and the Bonferroni method will be used to correct α , $\alpha' = \alpha/\text{comparison times}$.
- The rank sum test will be used for the data of unknown or non-normal distribution, and the difference is considered to be statistically significant when the test level is $\alpha=0.05$ ($P\leq 0.05$). Pairwise comparison using Bonferroni method to correct α , $\alpha' = \alpha/\text{comparison times}$

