8.7 Immunogenicity Analysis

- Specific antibody against S protein of SARS-CoV-2 (ELISA method) (day 0, day14, day 28, and month 6).
 - The geometric mean titer (GMT) of each visit in each group is described by numbers, geometric mean, standard deviation, median, quartile, maximum and minimum, etc.
 - Count the conversion rate of each group, expressed by the number and percentage, and calculate the 95%CI of the conversion rate.
 - The geometric mean fold increase (GMI) of each visit in each group is described by effective numbers, geometric mean, standard deviation, median, quartile, maximum and minimum, etc.
 - Stratification analysis is carried out according to the level of Ad5 antibody before immunization ($Ad5 > 200$, $Ad5 \leq 200$).
 - The continuous index is compared by analysis of variance between groups, and the pairwise comparison between groups is carried out by SNK method.
 - Chi-square test or Fisher's exact test is used to compare the classification index between groups, and chi-square segmentation/Fisher's exact test is used for pairwise comparison between groups.
 - Draw a reverse cumulative distribution map

- Specific neutralizing antibody against SARS-CoV-2 (neutralization test with live SARS-CoV-2 and its pseudovirus) (day 0, day 28, and month 6).
 - The geometric mean titer (GMT) of each visit in each group is described by numbers, geometric mean, standard deviation, median, quartile, maximum and minimum, etc.
 - Count the conversion rate of each group, expressed by the number and percentage, and calculate the 95%CI of the conversion rate.
 - The geometric mean fold increase (GMI) of each visit in each group is described by effective numbers, geometric mean, standard deviation, median, quartile, maximum and minimum, etc.
 - Stratification analysis is carried out according to the level of Ad5 antibody

before immunization ($Ad5 > 200$, $Ad5 \leq 200$).

- The continuous index is compared by analysis of variance between groups, and the pairwise comparison between groups is carried out by SNK method.
 - Chi-square test or Fisher's exact test is used to compare the classification index between groups, and chi-square segmentation/Fisher's exact test is used for pairwise comparison between groups.
 - Draw a reverse cumulative distribution map
- Specific neutralizing antibody of Ad5 (day 0, day 28, and month 6).

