- The geometric mean titer (GMT) of each visit in each group is described by numbers, geometric mean, standard deviation, median, quartile, maximum and minimum, etc.
 - Count the positive rate of Ad5 in each group, expressed by the number and percentage, and calculate the 95%CI of the positive rate.
 - The geometric mean fold increase (GMI) of each visit in each group is described by effective numbers, geometric mean, standard deviation, median, quartile, maximum and minimum, etc.
 - Stratification analysis is carried out according to the level of Ad5 antibody before immunization ($Ad5 > 200$, $Ad5 \leq 200$).
 - The continuous index is compared by analysis of variance between groups, and the pairwise comparison between groups is carried out by SNK method.
 - Chi-square test or Fisher's exact test is used to compare the classification index between groups, and chi-square segmentation/Fisher's exact test is used for pairwise comparison between groups.
 - Draw a reverse cumulative distribution map
- Detection of IFN- γ stimulated by S protein overlapping peptide library by ELISpot (day 28).
- The ELISpot of each group and each visit is used to detect the level of IFN- γ

stimulated by S protein overlapping peptide library, which is described by numbers, mean, standard deviation, median, quartile, maximum, minimum, and 95%CI, etc.

- Count the positive rate of ELISpot of each group and each visit, expressed by the number and percentage, and calculate the 95%CI of the positive rate.
- Stratification analysis is carried out according to the level of Ad5 antibody before immunization ($Ad5 > 200$, $Ad5 \leq 200$).
- Rank sum test is used for comparison of IFN- γ levels among groups, Wilcoxon rank sum test is used for pair comparison between groups adjusted by Bonferroni method.
- Chi-square test or Fisher's exact test is used to compare the positive rate between groups, and chi-square segmentation/Fisher's exact test is used for pairwise comparison between groups.
- Draw a bar chart of the level and positive rate of cellular response.
- Make statistics according to the positive and negative test results provided by the testing organization

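### The Ad5 antibody GMT and GMI comparisons are not adjusted for the day-0 Ad5 titre already collected; both tests are valid, but ANCOVA would be more precise and give one answer

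*SAP*

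**What the plan says.** SAP section 5.2.2 lists two Ad5 outcomes among the secondary endpoints: "Geometric mean titer (GMT) of neutralizing antibody against Ad5 at day 28, and month 6" and "Geometric mean fold increase (GMI) of neutralizing antibody against Ad5 at day 28, and month 6". Section 8.7 heads the corresponding block "Specific neutralizing antibody of Ad5 (day 0, day 28, and month 6", so each participant's baseline value is collected.

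For the group comparison that block says: "The continuous index is compared by analysis of variance between groups, and the pairwise comparison between groups is carried out by SNK method". The general rule in section 8.1 is the same: "The continuous variables will be analyzed by analysis of variance". Neither place names a covariate.

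The day-0 Ad5 titre is used in two other ways. It is the denominator of the GMI. It also defines a subgroup split at 200: "Stratification analysis is carried out according to the level of Ad5 antibody before immunization".

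**The concern.** For the SARS-CoV-2 titres, entry requires negative serology (section 3.5), so the outcome's own baseline should vary little. The Ad5 titre is different. No entry criterion restricts it, and the SAP's cut at 200 presumes a real spread at day 0. Randomisation is by block with no stratification on Ad5 stated (section 3.4.1), so day-0 titres can differ between arms by chance.

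On the log scale, the two planned comparisons handle that baseline in two fixed ways:

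- **GMT:** compares follow-up titres and gives day 0 a coefficient of 0.
- **GMI:** compares follow-up minus day 0, which fixes the coefficient at 1.

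If people with high titres stay relatively high but rise less, the true slope is between these values and each test carries avoidable noise. Two tests of one question will also be reported, and they can differ for no reason but baseline imbalance. What is at stake is how clearly the trial shows the anti-vector response by dose, above all middle versus low dose, where the difference may be small.

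**Working it through.** **Inputs from the SAP.** Section 3.3: 250 middle dose, 125 low dose, 125 placebo (250 + 125 + 125 = 500). Section 8.1: test level 0.05, taken here as two-sided. The sample size was not calculated, so the plan has no power figure to reproduce.

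**Assumptions (not in the SAP).** ANOVA is done on log titres. The correlation rho between day-0 and follow-up log titre is 0.3, 0.5 or 0.7. SDs at the two visits are equal unless stated. The middle-low difference is set so that the GMT test has 80% power. Power is for one pairwise test at 0.05, without the SNK step.

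**Step 1. Variance per person, follow-up SD = 1.**

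- GMT: 1
- GMI: 2(1 − rho)
- ANCOVA: 1 − rho²

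**Step 2. Anchor effect.** The standard error factor is √(1/250 + 1/125) = √0.012 = 0.1095. The effect is (1.960 + 0.842) × 0.1095 = 0.307 SD.

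**Step 3. Power** = Φ(2.802/√variance − 1.960).

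| rho | GMI variance | ANCOVA variance | GMT power | GMI power | ANCOVA power | Gain over better planned test |
|---|---|---|---|---|---|---|
| 0.3 | 1.40 | 0.91 | 80% | 66% | 84% | 4 points |
| 0.5 | 1.00 | 0.75 | 80% | 80% | 90% | 10 points |
| 0.7 | 0.60 | 0.51 | 80% | 95% | 97.5% | 2 points |

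If the follow-up SD is 0.8 of the day-0 SD, the GMI variance is 1 + 1/0.64 − 2·rho/0.8. GMI power becomes 55%, 69% and 87.5% at the three correlations, while GMT and ANCOVA are unchanged. The gain over the better planned test is then about 4, 10 and 10 points.

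**Step 4. Unequal slopes.** A three-arm simulation (4,000 runs) assumed slopes of 0.4 in both vaccine arms and 0.85 in placebo. For middle minus low, the SD of the estimate was 0.107 (GMT), 0.120 (GMI) and 0.099 (ANCOVA). The variance cut against GMT is 1 − (0.099/0.107)² = 0.14. Power at the same anchor is Φ(2.802 × 0.107/0.099 − 1.960) = Φ(1.07), about 86%. For middle minus placebo the SDs were 0.108, 0.082 and 0.078.

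**Step 5. How far the two planned estimates can differ.** With complete data, the middle/low GMT ratio divided by the middle/low GMI ratio equals the middle/low day-0 GMT ratio exactly. The edge of the chance 95% range for that ratio is 10^(1.96 × SD × 0.1095). For an assumed day-0 SD of 0.6, 0.8 or 1.0 log10 this is 1.35, 1.49 or 1.64 fold in either direction.

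In 200,000 simulated draws with equal SDs, the GMT and GMI tests gave different significance verdicts in 27%, 22% and 20% of trials (rho 0.3, 0.5, 0.7) at the 0.307 SD effect. With no true difference the figure was 7% to 9% (rho 0.3 to 0.9). Each test kept its 5% error rate.

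**Step 6. Does ANCOVA remove the disagreement?** Subtracting the day-0 value from the outcome shifts the baseline slope by exactly 1 and leaves the group differences unchanged. A fitted example confirmed this: identical group terms, with slopes of 0.498 and −0.502.

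**The case against.** The strongest reply is that nothing here is invalid. Chance baseline imbalance is already counted in the ANOVA standard error, and each test holds its 5% level. This stands. A reader might infer that imbalance biases the Ad5 results or that the planned tests are wrong; the documents support neither.

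A reader might also infer that the plan ignores the day-0 titre. It does not. The GMI contains it for every participant, and the split at 200 gives baseline-specific results. What is missing is adjustment of the overall comparison. Stratum results on a dichotomised baseline do not supply that.

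The size is assumption-bound, and that also stands. The 10-point gain over the better planned test needs rho near 0.5 with equal SDs, or a moderate to high correlation with unequal SDs. With a large true difference every method detects it, and with a negligible one none does. The 20% to 27% discordance counts significance verdicts at a borderline effect, so it should not be read as contradictory findings. The 1.35 to 1.64 fold figures are edges of a range, not typical values.

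Finally, these are two items in a long secondary list. The primary endpoints are untouched, and the SAP ties no decision rule to the Ad5 comparison.

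**Conclusion.** The point holds as a gain in precision and coherence. The SAP itself fixes an unadjusted ANOVA for both Ad5 outcomes while collecting the covariate that would sharpen it. The coefficients 0 and 1 cannot both be right, and for any slope strictly between them both tests lose to ANCOVA. The direction of the gain therefore does not depend on the exact correlation; its size does. Under the ranges shown, it is about 2 to 10 points of power over the better planned test. It is about 6 points over GMT for middle versus low dose in the unequal-slope case. Severity is low: a cheap improvement to a secondary analysis.

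**What to change.** In the Ad5 block of section 8.7, make the between-group comparison at day 28 and at month 6 an ANCOVA:

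- **Model:** log10 Ad5 titre on group and centred log10 day-0 Ad5 titre, with a group-by-baseline term and robust standard errors, because slopes may differ between vaccine and placebo.
- **Report:** adjusted GMT ratios (middle/low and each dose/placebo) with 95% CI. The adjusted GMI comparison gives the same ratios.
- **Multiplicity:** state a pairwise rule to replace SNK, for example the Bonferroni correction the SAP uses elsewhere. This choice has a price. At 0.05/3 the critical value is 2.394, and ANCOVA power at rho 0.5 becomes Φ(2.802/√0.75 − 2.394) = Φ(0.84), about 80% instead of 90%. The rule should be chosen with that in view.
- **Linearity:** check it, because section 5.2.2 replaces values below the detection limit by half the initial value and caps high values at the maximum dilution.
- **Keep as descriptive:** raw GMT, raw GMI and the results by stratum at 200.

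The cost is SAP wording and a few lines of SAS code before database lock, with no new data, visits or participants. One small downside: participants without a day-0 Ad5 result leave the GMT comparison, as they already leave the GMI comparison.

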8.8 Exploratory Aanalysts

- Analysis of the consistency of humoral immunity.
 - Linear regression is used to evaluate the consistency of specific antibodies against S protein of SARS-CoV-2 (ELISA method) and specific neutralizing antibodies (neutralization test with live SARS-CoV-2 and its pseudovirus). 95% confidence interval for calculating intercept and slope.
 - Taking the results of ELISA method as dependent variables and the values of neutralization test with live SARS-CoV-2 and its pseudovirus as independent variables, the scatter plot is drawn and the pearson correlation coefficient is marked.

- Analysis of persistence of humoral immunity.

- The geometric mean titer (GMT) of each group at month 6 is described by effective numbers, geometric mean, standard deviation, median, quartile, maximum and minimum.
- Count the conversion rate of each group at month 6, expressed as the number and percentage, and calculate the 95%CI of the conversion rate.
- The geometric mean fold increase (GMI) of each group at month 6 is described by effective number, geometric mean, standard deviation, median, quartile, maximum and minimum, etc. The detection value is described by the number of effective numbers, geometric mean, standard deviation, median, quartile, maximum, minimum and so on.
- The continuous index is compared by analysis of variance between groups, and the pairwise comparison between groups is carried out by SNK method.
- Chi-square test or Fisher's exact test is used to compare the classification index between groups, and chi-square segmentation/Fisher's exact test is used for pairwise comparison between groups.

8.9 Analysis Plan

8.9.1 First analysis

After the last participant completes visit 2 (28 days after immunization), and the study database is entered, reviewed and locked, it can be handed over to the independent statistical party for the first analysis. The first statistical analysis report must be reviewed by the DSMB to determine that the report is carried out in strict accordance with the first statistical analysis plan before it can be submitted to the investigators and sponsors.

8.9.2 Final analysis

After the last participant completes visit 3 (month 6), collect the data of serious adverse events, humoral immunity and cellular immunity from visit 2 (day 28) to visit 3 (month 6), and carry out final statistical analysis and summary.

9 Statistical tables

See CM20200407 a phase II clinical trial of the recombinant novel coronavirus vaccine_tableshell_V1.0_20200518.
